2.3 Secondary Outcome Measures

In addition to the clinical outcomes, plaque samples and peri-implant sulcular fluid (PISF) will be taken to assess the microbiologic and immunologic profile before and after treatment with or without aPDT. Subgingival biofilm samples will be collected using sterile titanium implant scalers and will be assessed at baseline and week 12 follow up. PISF will be collected from the tested implant site after clinical examination. The levels of interleukin (IL)-1 α , IL-1 β , IL-6, IL-8, IL-10, IL-12, IL-7A, tumor necrosis factor (TNF)- α , C-reactive protein, osteoprotegerin, leptin, and adiponectin will be determined using multiplex proteomic immunoassays.

2.4 Potential Risks and Benefits:

a. End Point – Efficacy

All eligible patients needing non-surgical treatment of peri-implant disease will receive the appropriate treatment of mechanical debridement. The mechanical removal of plaque around the implants is the gold standard of care in the treatment of implant inflammation. The patients in the adjunctive aPDT group may have improved healing as observed through surrogate clinical measures of inflammation (BOP, PPD), greater microbiologic reduction, and levels of key biomarkers in PISF that resembles peri-implant tissue health (Recker 2015).

b. End Points – Safety

1) Study related risks:

Initial mild pain, swelling, and bleeding related to non-surgical implant surface mechanical debridement. Potential for antimicrobial methylene blue dye to reversibly stain gingiva around implant site. Collecting PISF will not result in any additional side effects. Patient will not be provided medications for study

related pain. If patient reports pain after treatment will recommend over the counter analgesics such as ibuprofen or acetaminophen.

2) Protection against risk:

All efforts will be made to minimize risks to all and every participant. Laser safety protocols will be followed including laser safety mechanisms, labels and signage, safety zone implementation, proper eye protection for patient and clinician.

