6.3 Study Visits and Procedures

a. Screening Visits and Procedures

Study protocol and consent forms will be approved by the Institutional Review Board at the University of Texas Health Science Center at Houston. The trial will be registered with ClinicalTrials.gov. The clinicians treating patients at UTSD will be told the information of this clinical trial. The potential subjects will be identified in the clinic of Department of Periodontics, Prosthodontics, or UTDentists for initial screening. The principal investigator will confirm the eligibility of these patients.

All patients will sign the consent forms and will be informed of the details of study procedures as well as potential complications. After informed consent is obtained, the non-surgical implant therapy will be scheduled as the first visit.

Patient's Demographic Data Collection

Upon enrollment into the study and patient's consent form signed, patient's demographic data from patient's electronic health record (EHR) in the UT School of Dentistry will be collected. This information will include, but not limited to, patient's de-identifiable chart number, age, gender, race, medical history, dental conditions, and all pertinent dental implant related data. Radiographic information regarding the implant(s) included in the study will also be collected prior to treatment.

b. Study Visits and Procedures

Patients will be randomly divided into 2 treatment groups. (A) Test group: patients will undergo traditional non-surgical mechanical debridement with adjunctive use of aPDT at implant(s). (B) Control group: patients will undergo traditional non-surgical mechanical debridement alone with “sham” aPDT with saline and non-light emitting laser at implant(s). Clinical measurements and PISF will be collected at the baseline appointment, and at follow up 12 weeks after treatment. For PISF collection, the volume of fluid collected will be measured using Periotron then stored in -80° C freezer. Plaque samples will be taken at baseline and at the 12-week appointment. Full mouth prophylaxis or periodontal maintenance will be completed with ultrasonics, hand instruments, and prophylaxis paste. Oral hygiene instructions will be

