9.2 Collecting, Recording and Reporting of Adverse Events

Examination and close follow-up of parameters capturing subjects' oral health will be collected on case report forms (CRFs). These will be completed at every study visit, and data will be compiled into a pre-specified format and reviewed monthly by the PI for safety oversight. Serious adverse events (as defined in Section 9.1) will be collected from the time of enrollment until the last clinic visit and will be recorded in the electronic health records (EHR) system. At each study visit, the clinician or investigator will inquire

about the occurrence of SAEs since the last assessment. The investigator will review all source documentation related to study procedures for evidence of SAEs. Events will be followed for outcome information until they return to baseline or stabilize, or until 30 days after study completion or subject discontinuation. Subjects who have an SAE that is ongoing 30 days after study completion or discontinuation will be referred to an appropriate practitioner for continued care. Upon learning that a subject has experienced an SAE, the investigator must report the event to CPHS within 24 hours after becoming aware of the event.

On a monthly basis, the following events will be reported to every PI:

- Number of subjects experience severe complications and number of subjects enrolled. Severe complications include severe pain, continuous bleeding and severe swelling that needs prescription to control.
- Duration of observation of subjects experiencing severe complications and duration of observation of subjects enrolled.
- Any tooth loss, abscess, or other adverse oral health development requiring therapy or other intervention and the etiology (as captured in the dental history)
- Every PI will review the monthly reports for any safety signals.

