11.2 Statistical and Analytical Plans

a. General Consideration

We will present means and standard deviations for completeness of the report. The statistical significance level to test the primary endpoint was set at $p<0.05$.

b. Safety Analyses

Safety will be evaluated by tabulations of adverse events and will be presented with descriptive statistics at baseline and follow-up visits each month.

Adverse events will be classified as severe complications and summarized for baseline and follow-up visits.

All information pertaining to adverse events noted during the study will be listed by subject, detailing verbatim given by the investigator, preferred term, date of onset, date of resolution, severity, and relationship to procedure. The onset of adverse events will also be shown relative (in number of days) to the day of performing the surgery.

c. Statistical Analysis Plan

We will analyze these data sets using generalized linear mixed effects models with the appropriate error structure (e.g., binomial, poisson) and specifying treatment (control mechanical debridement vs mechanical debridement + aPDT) as a fixed factor and repeated measures of individuals over 0, 6, and 12 weeks as a random factor. Demographic data collected from patients will be included in analysis and will be adjusted for any confounders. All quantitative analyses will be performed in R Statistical Software (R Core Team 2017).

For microbiologic analysis, microbial DNA will be purified using the QIAmp DNA Mini Kit (Qiagen, Hilden, Germany) or Qiagen DNA MiniAmp kit (Qiagen, Valencia, CA, USA), according to the manufacturer's protocol. 16S rRNA gene V4 amplification and sequencing will be completed. 16S rRNA gene data analysis will also be completed for the plaque samples.

For immunologic analysis, the PerioPaper strips will be analyzed using multiplexed fluorescent bead-based immunoassay. Assessments will be made in triplicate, and for the statistical analysis, median of the replicates will be used.

12. Ethical Consideration

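### Section 11.2b labels adverse events as severe complications and lays out its summaries by visit with no treatment arm, so the plan as written does not show what harm aPDT adds to debridement

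*Combined protocol and SAP*

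**What the plan says.** Section 11.2b sets out the safety analysis in four steps.

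- Layout: "Safety will be evaluated by tabulations of adverse events and will be presented with descriptive statistics at baseline and follow-up visits each month".
- Classification: "Adverse events will be classified as severe complications and summarized for baseline and follow-up visits".
- Listing: "All information pertaining to adverse events noted during the study will be listed by subject". For each event the listing gives the investigator's wording, a preferred term, start and end dates, severity and relation to the procedure. Treatment arm is not among the named fields.
- Timing: "The onset of adverse events will also be shown relative (in number of days) to the day of performing the surgery".

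Section 9.2, on the monthly reports, says: "Severe complications include severe pain, continuous bleeding and severe swelling that needs prescription to control". Section 2.4b describes the expected study risks as "Initial mild pain, swelling, and bleeding related to non-surgical implant surface mechanical debridement", together with possible reversible staining of the gingiva by the dye. Section 6.3a describes the treatment session: "After informed consent is obtained, the non-surgical implant therapy will be scheduled as the first visit".

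**The concern.** The classification sentence takes a term that 9.2 uses for severe events and applies it to adverse events in general. The reactions that 2.4b tells patients to expect are mild or reversible, so they do not fit. A programmer following 11.2b has two options: enter mild events under a heading that calls them severe, or omit them because they do not meet the heading. Either way the summary misstates the severity profile.

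The second matter is the comparison. Both arms receive debridement; they differ in dye versus saline and in whether the laser emits light. The safety question is therefore what dye and light add. The plan itself names one risk that only the test arm carries, dye staining. Yet no planned safety summary is specified by arm.

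**Working it through.** The safety section states no figure to reproduce, so the main check is of wording.

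**1. The label**

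| Place | What it implies for a mild, transient event |
|---|---|
| 2.4b | Expected: mild pain, swelling, bleeding; reversible staining |
| 9.2 | Not among the examples given for severe complications |
| 11.2b, listing | Recorded with its own severity |
| 11.2b, classification sentence | Classified as a severe complication |

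The last row cannot be reconciled with the other three. A per-event severity entry has no purpose if every event is severe by classification.

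**2. The arm.** The 11.2b summaries are by visit, and its listing is by subject. The monthly report in 9.2 sets subjects with severe complications against subjects enrolled, without a split. The mixed model in 11.2c has treatment as a fixed factor, but it is written for measures repeated at 0, 6 and 12 weeks and does not name adverse events.

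**3. What a table without arms hides (assumed counts).** Section 3.1 gives 32 patients per group, 64 in all. Suppose 6 patients have an event.

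- Split 3 and 3: all patients 6/64 = 9.4%; risk difference 3/32 − 3/32 = 0.
- Split 0 and 6: all patients 6/64 = 9.4%; risk difference 6/32 − 0/32 = 18.8 percentage points. Fisher exact p = 2 × C(32,6)/C(64,6) = 2 × 906,192/74,974,368 = 0.024.

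The overall line is identical; only a by-arm table separates the two cases.

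**4. What a by-arm table can support**

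- With no events in an arm of 32, the one-sided 95% upper limit is 1 − 0.05^(1/32) = 8.9%.
- For assumed true rates of 10% and 30%, with two-sided alpha 0.05, the standard error under the null is √(2 × 0.20 × 0.80/32) = 0.100 and under the alternative √((0.10 × 0.90 + 0.30 × 0.70)/32) = 0.0968. Power is Φ((0.20 − 1.96 × 0.100)/0.0968) = Φ(0.04) = 52%.

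The table would therefore be descriptive.

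**5. Whether mild events reach the table.** The visit inquiry in 9.2 asks about SAEs. Section 9.1 defines an SAE as an unanticipated problem, which must among other things be unexpected. Mild pain or staining foreseen in 2.4b does not meet that definition. Section 11.2b nevertheless lists all adverse events noted. The two sections describe different collection scopes.

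**6. The time origin.** Section 6.3 describes one non-surgical treatment session. Section 6.3d also refers to outcomes of a surgery, and sections 8.2 and 9.3 use operative wording for the aftercare. The word in 11.2b reads as leftover wording for that single session.

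**The case against.** The strongest reply is that the data needed are already planned. The by-subject listing carries severity and relation to the procedure for each event, and allocation is known, so a by-arm table by severity could be produced later. That stands. A reader might infer that the safety analysis is unable to show added harm; the documents support only that no such display is planned. What remains is that an unplanned regrouping leaves its layout to be chosen after the data are seen.

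It can also be said that 9.2 says severe complications include three items, which is not a closed definition, and that it reports tooth loss, abscess and other oral events needing treatment separately. That is fair: safety reporting as a whole does not rest on one label. But an open list of severe events still does not take in mild ones.

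The monthly counts over all enrolled subjects are oversight reports to the PI. They do not show that the final analysis will pool the arms; on that 11.2b is silent. A reader might also infer that onset times have no origin because no study surgery takes place. With a single treatment session, the intended day is clear in practice, and this is a wording slip.

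**Conclusion.** The point holds in a limited form. The classification sentence in 11.2b contradicts 9.2, 2.4b and the section's own severity entry, and applying it literally would mislabel or drop mild events. The summaries as laid out do not plan to show what aPDT adds to debridement.

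Its size cannot be put as a number of misclassified events: the documents give no adverse event rate, and mild events may not be collected systematically. Nor do they plan a pooled confidence limit that could be criticised as too narrow. The 9.4% example rests on assumed counts and shows only that an overall figure can be the same with a risk difference of 0 or 18.8 percentage points. The primary efficacy analysis is unaffected. The change should be made, since it is specific and cheap.

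**What to change.** In section 11.2b:

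1. Replace the classification sentence with: 'Adverse events will be summarised by the severity recorded in the listing. Severe complications, as the term is used in section 9.2, will be shown as a separate row.'
2. Add: 'For each treatment arm, the number and percentage of patients with at least one adverse event will be tabulated by severity.' The table is descriptive; a risk difference with its interval is optional.
3. As a wording correction only, count onset from the day of study treatment in place of "relative (in number of days) to the day of performing the surgery".

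Reconcile the visit inquiry in 9.2, which covers SAEs only, with the listing of all adverse events in 11.2b, and state which non-serious events are collected and how. Without this the lower-severity rows may be empty for lack of asking.

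The cost is SAP wording and one table layout, plus some added data collection if the reconciliation widens the inquiry. Sample size, visits and treatment do not change. The downside is that per-arm estimates are less precise than figures for all patients, and the comparison is descriptive, not powered.

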2.2 Primary Outcome Measures

This study aims to compare clinical outcomes (change in BOP and PPD) after mechanical debridement of implant surfaces at sites exhibiting plaque induced inflammation with or without adjunctive aPDT. Bleeding on probing and periodontal probing depths will be assessed clinically through a periodontal probing exam at baseline, week 6, and week 12 follow up. Probing depth reduction endpoint value of 1mm (Bassetti et al. 2014, Morrison et al. 1980). Bleeding on probing endpoint value of 50-60% reduction of sites with BOP (Bassetti et al. 2014). Demographic and implant related variables will be analysed using multivariate analysis for correlation with peri-implant mucositis and peri-implantitis.

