5. STUDY DESIGN

5.1 Summary of Study Design

This is randomized double blinded clinical control study designed to assess improved clinical and microbiological outcomes with the use of laser antimicrobial photodynamic therapy (aPDT) as an adjunct to the gold standard of mechanical debridement in the treatment of peri-implant diseases. Seventy-four patients will be recruited. Clinical measurements including bleeding on probing, pocket depth, plaque, and clinical attachment will be measured at baseline, 6 weeks, and 12 weeks after therapy. The 2017 World Shop classification will be used to diagnosis implants as peri-implant mucositis or peri-implantitis (as stated above in section 3.3). Only diseased implants will be included and only one implant per patient will be studied. The hypothesis is that inflamed implant sites treated with mechanical debridement and adjunctive aPDT will have greater reduction in bleeding and pocket depth reduction than those sites treated with mechanical debridement alone. The potential for greater healing and greater antibacterial activity on the implant surface will benefit patients who have peri-implant diseases. The results can be applied in the managing and in the armamentarium for treatment of both peri-implantitis and peri-implant mucositis.

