6. METHODS AND ASSESSMENTS

6.1 Randomization and Blinding

Therapy group allocation (test or control) will be performed by the investigators before treatment is rendered based on computer-generated randomized (R Statistical Software). Two blinded examiners will be used to take clinical measurements (presence/absence of Plaque, BOP, PPD, CAL) at baseline, and then six and twelve weeks after treatment. Patients in the control group will be blinded by performing mechanical debridement plus a “sham” aPDT (saline with non-light emitting laser).

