reviewed with all patients including techniques to clean around implants. Mechanical debridement of implant surfaces will be completed with titanium scalers and ultrasonics removing supragingival and subgingival plaque. Antimicrobial photodynamic therapy will be done at implant sites by applying a photosensitizing dye methylene blue (0.1 mg/ml) with a disposable syringe from the bottom of pocket in a coronal direction. The methylene blue dye will be diluted from 1.0% to 0.1% before use. The dye will be applied topically confined to the epithelialized space surrounding the implant fixture and will not be internalized. After 5 minutes in situ, the surrounding gingival tissues will be irradiated at six sites around the implant using a diode laser with a wavelength of 660nm, providing an energy density of 10 J/site, 100mW power, time equal to 100 seconds. After irradiation, the site will be thoroughly rinsed with saline. Only pockets \geq 4mm will be treated with the diode laser as this is the threshold pocket for diagnosing peri-implant inflammation per the 2017 World Work Workshop (Heitz-Mayfield & Salvi, 2018).

Clinical Measurements

Implant sites will be evaluated at baseline, six weeks, and twelve weeks after treatment (2 follow-up visits in total). Improvement in sites resulting from a reduction in inflammation will be analyzed based on pocket depth, clinical attachment loss, bleeding on probing, and the presence of plaque. For clinical measurements, six sites around the implant will be measured: mesial buccal, mid buccal, distal buccal, mesial lingual, mid lingual, and distal lingual. Bleeding on probing will be evaluated by gently sweeping the periodontal probe just within the gingival sulcus of the implant and the presence or absence of bleeding will be recorded. The presence or absence of plaque will then be evaluated at six sites around the implant surface. Plaque sampling will be performed prior to the remaining clinical measurements at the baseline/treatment appointment and 12 weeks after treatment utilizing a titanium curette within the gingival sulcus of the inflamed site. Periodontal pocket depth is measured from the free gingival margin to the base of the pocket, with a UNC periodontal probe with 1mm measurement units. Clinical attachment loss is measured by subtracting the pocket depth from distance of the free gingival margin to the implant platform.

Microbiologic collection and analysis

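### The only efficacy model (Section 11.2c) puts pre-treatment week 0 among the responses and names no visit term, baseline covariate or primary contrast, so it does not pin down an estimate of change in BOP and PPD

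*Combined protocol and SAP*

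**What the plan says.** Section 2.2 states the primary aim: "This study aims to compare clinical outcomes (change in BOP and PPD) after mechanical debridement of implant surfaces". It adds a benchmark, "Probing depth reduction endpoint value of 1mm". Section 5.1 words the hypothesis the same way: test sites "will have greater reduction in bleeding and pocket depth reduction than those sites treated with mechanical debridement alone". Section 6.1 has the blinded examiners measure "at baseline, and then six and twelve weeks after treatment", so week 0 precedes treatment.

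Section 11.2c is the only place that gives an efficacy model. It is a generalized linear mixed model with treatment "as a fixed factor and repeated measures of individuals over 0, 6, and 12 weeks as a random factor". The error structure is left to be chosen, with binomial and Poisson as examples. The next sentence brings in demographic data and adjustment for confounders. Section 11.2a sets a 0.05 significance level for the primary endpoint without saying which outcome, visit or contrast that is.

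The visit schedules differ by outcome. Sections 2.2, 5.1, 6.1 and the Clinical Measurements part of 6.3 put clinical measurements, over six sites per implant ("six sites around the implant will be measured"), at weeks 0, 6 and 12. Section 6.3b omits week 6: "Clinical measurements and PISF will be collected at the baseline appointment, and at follow up 12 weeks after treatment". Microbiology has two time points: "Plaque samples will be taken at baseline and at the 12-week appointment".

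**The concern.** The outcome is a change, but the model sentence names neither a change nor a follow-up contrast. Treatment is the only fixed design factor named, and the baseline visit is one of the responses. Adjusting for demographic confounders does not help, because baseline BOP or PPD is not demographic data.

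Two consequences are possible, depending on how the sentence is applied. If the analyst adds visit terms, nothing in the plan says which visit or contrast carries the 0.05 test, and that choice can be made after the data are seen. If the analyst follows the sentence as it stands, the treatment coefficient averages over a visit at which no effect can exist. It then understates the follow-up effect, and it carries any chance baseline imbalance into the result.

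**Working it through.** **Inputs from the documents.** 64 evaluable patients, 32 per arm; alpha 0.05 (two-sided assumed); 80% power for a large effect, with no number attached (Sections 3.1, 11.1); visits at weeks 0, 6 and 12.

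**Assumptions.** SD 1 at each visit, compound symmetry with correlation r, identity link, complete data, normal approximation. The documents give no SD, correlation or effect pattern, so r runs from 0.1 to 0.7.

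**The plan's own figure.** With 32 per arm, 80% power is reached at d = 0.70 (normal) or 0.71 (t test). At the conventional large value d = 0.8, which is an assumption, power is 89% (normal) or 88% (t). Both 0.71 and 0.8 are used below.

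**What the literal model estimates.** The expected arm difference at week 0 is zero under randomisation, so the main effect is (0 + d6 + d12)/3.
- Equal effect at weeks 6 and 12: 2d/3. An added 1 mm PPD reduction would read as 0.67 mm.
- Half the effect at week 6: (0 + 0.5d + d)/3 = 0.50d.
- Effect at week 12 only: d/3.

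**Power.** SE = sqrt(2 × factor / 32), with these factors:
- As written: (1 + 2r)/3, estimate 2d/3
- Baseline-adjusted mean of weeks 6 and 12: (1 + r)/2 − r², estimate d
- Baseline-adjusted week 12: 1 − r², estimate d

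Example, d = 0.71, r = 0.5. As written: estimate 0.473, SE sqrt(2 × 0.667/32) = 0.204, ratio 2.32, power 64%. Adjusted mean: estimate 0.71, SE sqrt(2 × 0.5/32) = 0.177, ratio 4.02, power 98%.

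Equal effect at weeks 6 and 12:

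| d | Analysis | r=0.1 | r=0.3 | r=0.5 | r=0.7 |
|---|---|---|---|---|---|
| 0.71 | As written | 85% | 74% | 64% | 56% |
| 0.71 | Adjusted mean | 97% | 97% | 98% | >99% |
| 0.71 | Adjusted week 12 | 81% | 84.5% | 91% | 98% |
| 0.80 | As written | 92% | 83% | 74% | 67% |
| 0.80 | Adjusted mean | 99% | 99% | 99% | >99% |
| 0.80 | Adjusted week 12 | 90% | 92% | 96% | 99% |

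Since (1 + r)/2 − r² = (1 + 2r)(1 − r)/2, the squared estimate-to-SE ratio of the adjusted mean exceeds that of the as-written test by a factor 1.5/(1 − r). That is at least 1.5 for any r from 0 upwards. Adjusted week 12 overtakes the as-written test where 4(1 − r²) = 3(1 + 2r), that is 4r² + 6r − 1 = 0, so r = 0.15.

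If the effect appears only at week 12 (d = 0.71, r = 0.3/0.5/0.7), power is 25/21/18% as written, 48/52/66% for the adjusted mean and 84.5/91/98% for adjusted week 12.

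**Baseline imbalance.** One standard error at baseline is sqrt(2/32) = 0.25 SD. It moves the as-written estimate by 0.25(1 + 2r)/3, which is 0.13/0.17/0.20 SD at r = 0.3/0.5/0.7.

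**Validity under the null.** In simulations with complete data the size of the as-written test was mostly 5.2 to 5.6%, with one conservative setting at 3.3%. With no visit term, a 1 SD fall over time, r = 0.5 and dropout of 5% against 25%, size was 7.9%; with a visit term it was 4.5%.

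**Open choice of contrast.** From 2,000,000 null draws per r, each single test having size 5%, the false-positive rate for one outcome is:
- Better of week-6 and week-12 change: 9.1%
- Better of baseline-adjusted week 6 and week 12: 9.3 to 9.7%
- With the pooled main effect as a third candidate: 13.6% (changes) or 12.6 to 13.2% (adjusted)

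**The case against.** The strongest reply is that the sentence is shorthand. Naming one fixed factor does not exclude visit, and the random factor may simply be a random subject effect. That is a fair reading, and it makes the dilution conditional. It does not remove the problem, because on that reading the visit and contrast are unstated and no other section supplies them.

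A reader might infer that the as-written test is invalid. The documents do not support that: with randomisation and balanced follow-up it is a valid test of no effect. Inflation needs clearly unequal dropout together with no visit term.

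A reader might also infer that the as-written test always has less power. It does not. Below r = 0.15 it beats baseline-adjusted week 12 (85% against 81% at r = 0.1, d = 0.71), and at d = 0.8 it still exceeds 80% up to r = 0.3. Only the adjusted mean of both visits is better at every correlation shown.

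The two-thirds factor belongs to an identity link. The plan's examples are binomial and Poisson; on logit or log scales the direction is the same but the factor is not exactly 2/3.

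Finally, it is tempting to say that plaque is measured at two visits only. That is true of the plaque samples and PISF. Clinical plaque presence or absence is also scored at week 6 (Sections 5.1, 6.1 and 6.3, Clinical Measurements).

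**Conclusion.** The point holds, and it should be fixed before the data are analysed. The firm part needs no assumptions: the only efficacy model names no visit, baseline covariate or contrast, includes a pre-treatment response, and so does not specify an estimate of the stated outcome.

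The size depends on the reading. If visit terms are intended, choosing between the two follow-up visits gives about 9 to 10% false positives per outcome. The figure of about 13% applies only if the pooled main effect is also a candidate. If the sentence is followed literally with an identity link, the reported effect is two thirds of an equal follow-up effect and one third of an effect seen only at week 12. The power loss against the adjusted mean is substantial throughout the range at d = 0.71 (12 points at r = 0.1, over 40 at r = 0.7), but it rests on the assumed SD, correlation structure and effect pattern. The documents do not show that the analysts will follow the literal reading.

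The missing week 6 in Section 6.3b is a wording slip against four other places and should be reconciled at the same time.

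**What to change.** Replace the model sentence in Section 11.2c with:

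> For BOP (bleeding sites out of six, binomial) and PPD (one patient-level summary named in advance, Gaussian), the responses are the week-6 and week-12 values. The model has fixed effects for treatment, visit, treatment-by-visit and the baseline value of that outcome, and a random subject effect. The primary contrast is [the treatment difference averaged over weeks 6 and 12, or the treatment difference at one named visit], fixed before any unblinded data are seen. For PISF analytes and for pre-named scalar summaries of the plaque-sample (16S) data, collected only at baseline and week 12, the week-12 value is compared between arms with its baseline value as covariate.

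The sponsor fills in the bracket and the PPD summary. The averaged contrast is the stronger choice if an effect is expected at both visits, the week-12 contrast if it is expected mainly at week 12. Clinical plaque presence or absence keeps its week-6 data and follows the BOP model. Correct Section 6.3b to agree with Sections 2.2, 5.1, 6.1 and the Clinical Measurements part of 6.3 on week 6.

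Cost: SAP wording and the IRB amendment review that Section 12.2 requires. No new data, visits or patients.
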